#### **C.3.d. Data Collection**

*Quantitative Data Collection* – The app will automatically collect number of visits to restaurants. It will also collect usage data such as how often participants submit pictures and whether they include annotations. In addition, as a gold standard, pre-post 24-hour food recalls will be performed to assess caloric intake. Post intervention sessions will be conducted to measure final heights and weights.

*Qualitative Data Collection* – At the completion of their 3-month participation (or earlier if drop out seems to have occurred – i.e., they do not use the app for a 3-week period), adolescents will participate in a semi-structured interview. Location data will be used to inform the questions in the interview. For example, participants who, based on the GPS, have not visited restaurants will be asked to share reasons for this change. Those who, based on the GPS, continue to visit restaurants will be asked about the choices made, and what if anything would be most helpful to them when they are making the choice regarding what to purchase. They will also be asked about the user interface, cultural tailoring, and the SNAP component.

#### **C.3.e. Analyses**

Primary Outcome – Calories purchased (by and for adolescents) will be assessed using annotated photos, and nutrition data from restaurant menus (e.g., if the participant submits a picture of McDonald’s fries and indicates that it is a small order, then from the McDonalds menu, we will determine that the calories purchased were 240 kcals). Number of visits will be obtained from the app. We will use population averaged generalized estimating equation regressions (GEE) to compare trajectories of calories purchased and number of visits between groups. The GEE approach allows us to account for the correlation in repeated observations collected from subjects over time. For calories purchased, we will perform GEE linear regression modeling as a function of time, treatment group (intervention vs. control) and the interaction of time by treatment group ( $Y = \beta_0 + \beta_1 Time + \beta_2 Treatment + \beta_3 Time * Treatment + \epsilon$ ). Residual diagnostics will be performed to examine departures from model assumptions. If needed, we will use transformed outcome variables and refit the models.

Secondary Analyses – Similarly, for the number of visits by the adolescents to restaurants, we will fit a GEE Poisson regression model as a function of time, treatment group (intervention vs. control group) and the interaction of time by treatment group. For change in BMI, we will perform multiple linear regression of change as function of initial BMI and treatment group. We will add participant characteristics to the models discussed above and explore associations between the outcomes and covariates of interest (e.g. extent of app use, initial BMI (adolescent and parent), race/ethnicity). In additional exploratory analyses, using methods described above, changes in calories purchased from restaurants as assessed by the 24-hour recalls will also be examined to compare findings with the photo documentation method of assessing calories. Pre-post changes in total calories reported via the 24-hour food recalls will also be calculated and compared between groups.

Power – The trial will be powered on average calories purchased in restaurants. The average child consumes 765 calories per meal eaten away from the home and the average child eats 2.5 meals per week away from the home. While the trial population eat out more often at baseline, this conservative estimate was used in the

power calculation. Programs for youth suggest benefits from a 250 kcal deficit per day. We determined that a clinically significant change would be a minimum decrease of 650 kcal/week. A sample size of 60 in each group (intervention vs. control group) will have 80% power to detect a difference of 650 kcal/week using a two group t-test with a two tailed alpha of 0.05 and a standard deviation of 1200 kcals. Thus by recruiting 75 adolescents per group even with a 20% attrition we will have the power to detect the expected results.

**Qualitative Analysis** –From the post-trial interviews and the satisfaction survey we will identify participants' perceptions of the intervention overall and of the messages specifically, using the qualitative methods described above. We will explore potential differences for parents' vs adolescents' and by race/ethnicity.

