### **C.3.c. Six-Week Intervention**

**Baseline Data:** For the first 2 weeks the app will only record presence in a restaurant and ask users to submit photos of their food. In week 3 the program features will be activated for the intervention group.

**Intervention Group:** *Point of Purchase (POP) messages will encourage healthy choices when participants are noted to be in a restaurant.* Participants will be asked to keep the app running on their phone. They will receive a ping when the app identifies that they are in a fast food restaurant followed by a POP prompt, tailored to their preferences and the options available at that location. If they are in a venue without a menu (though this is unlikely as most participants in the developmental project frequented popular franchises with published menus), general healthy suggestions will be provided (such as “consider choosing smaller portions” or “does this venue sell fruit?”). If the app does not ping when they enter a restaurant, they will be asked to register that location by tapping the ‘register location’ button on the app and entering the restaurant name. For detection errors, the appropriate stored venue criteria (location, geo-fence, time of day or dwell time) may be adjusted to improve detection. Users will also be asked to take a picture of any items they buy and to annotate it with information that would help to determine the nutrients in the food. Annotations may be audio, text, or made from a selection of descriptive buttons (e.g., to indicate small, medium or large sizes).

Tailored healthy lifestyle messages will be delivered at times selected by participants. In addition to messages prompting healthy choices at the point of sale, participants will receive tailored messages promoting healthy lifestyle choices. Participants will select the timeframe during which they would like to receive these daily messages. The messages will be tailored to their values, characteristics and preferences, and will address topics such as increased physical activity, obtaining sufficient sleep, and healthy nutrition. As described above, these messages will be based on Self Determination Theory and use motivational interviewing approaches.

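### The primary GEE does not define Time, the deciding coefficient or the role of weeks 1–2, and on a linear-week reading it does not test the 650 kcal/week mean difference on which the trial is powered

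*Combined protocol and SAP*

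**What the plan says.** Section C.3.e gives a single model for the primary outcome: "we will perform GEE linear regression modeling as a function of time, treatment group (intervention vs. control) and the interaction of time by treatment". Written out, it is Y = β0 + β1 Time + β2 Treatment + β3 Time×Treatment + ε. Its stated purpose is to "compare trajectories of calories purchased and number of visits between groups". The same methods are reused for the food recalls: "using methods described above, changes in calories purchased from restaurants as assessed by the 24-hour recalls will also be examined". C.3 places those recalls in the baseline week and the final week.

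The Power paragraph of C.3.e is about a mean: "The trial will be powered on average calories purchased in restaurants". It calls for "a clinically significant change would be a minimum decrease of 650 kcal/week" and claims "80% power to detect a difference of 650 kcal/week using a two group t-test with a two tailed alpha of 0.05", with 60 per group and an SD of 1200 kcal.

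Under Baseline Data, C.3.c says "For the first 2 weeks the app will only record presence in a restaurant and ask users to submit photos of their food", and then "In week 3 the program features will be activated for the intervention group".

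The length of follow-up is not settled. The C.3 overview and C.3.d say three months, while the heading of C.3.c says six weeks. C.3.b has dyads randomised at enrolment and told their group by phone message.

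**The concern.** The model does not say whether Time is a week number, a pre/post indicator or a set of categories, nor where it starts. It does not give the unit of Y, the working correlation, or which coefficient decides the trial. Nothing says whether weeks 1–2 are outcomes, a reference period, a covariate or excluded.

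At least four codings fit the text:

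- **Pre/post.** β3 is the difference in mean change, so it matches the powered quantity. The Baseline Data label, the power section's reference to a decrease, and the reuse of the methods for two-occasion recalls all point this way.
- **Linear week, weeks 1–2 included.** β3 is a difference in slope. The stated aim of comparing trajectories points this way.
- **Linear week from week 3.** β3 is a slope within the active period only.
- **Categorical week.** There are several interaction terms and no single test.

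These test different quantities on the same data, and an analyst could choose among them after seeing the data and still comply with the plan. The features switch on as a step in week 3, so a sustained benefit is a shift in level. A slope captures that only partly, or not at all.

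**Working it through.** **1. The plan's own figure.** The inputs are a difference of 650, SD 1200, two-sided alpha 0.05 and 60 per group (C.3.e, Power).
- n = 2(1.960 + 0.842)² × (1200/650)² ≈ 54 per group; the exact t-test gives 55.
- At n = 60 the standard error is 1200√(2/60) = 219.1 and 650/219.1 = 2.967, so power is 84.3% (exact t: 83.7%).
- 60/0.8 = 75.

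The stated size is therefore slightly conservative for a two-group comparison of means.

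**2. What β3 equals under each coding.** Benefits are written as positive reductions, zero in weeks 1–2. With independence or exchangeable working correlation, the linear-week coefficient is β3 = Σ(t − t̄)dₜ / Σ(t − t̄)². Three months is taken as 13 weeks, and the shorter version as 6 weeks in total.
- Pre/post, constant 650: β3 = 650.
- Linear, 13 weeks, constant 650: t̄ = 7, Σ(t − 7)² = 182, and Σ(t − 7) over weeks 3–13 is 11. So β3 = 650 × 11/182 = 39.3.
- Linear, 6 weeks, constant 650: t̄ = 3.5, Σ(t − 3.5)² = 17.5, and the sum over weeks 3–6 is 4. So β3 = 650 × 4/17.5 = 148.6.
- Linear from week 3 only, constant 650: β3 = 0, so the test rejects 5% of the time at any length.
- Linear, 13 weeks, fade 975 to 325 (mean 650, falling 65 per week): numerator 7150 − 65 × 110 = 0, so β3 = 0.
- Linear, 6 weeks, same fade (falling 216.7 per week): numerator 2600 − 216.7 × 5 = 1516.7, so β3 = 1516.7/17.5 = 86.7.

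**3. Power.** The documents give no within-person correlation. I assumed exchangeable 0.2–0.6 or AR(1) 0.5–0.8, Y as weekly kcal with weekly SD 1200, complete data and 60 per arm. S is the weekly covariance matrix.
- Slope: SE = √[(2/60) w′Sw], where w is the second row of (X′V⁻¹X)⁻¹X′V⁻¹, X = [1, week] and V is the working correlation. Example, exchangeable 0.2 at 13 weeks: SE = 1200√[2 × 0.8/(60 × 182)] = 14.5, 39.3/14.5 = 2.70, power 77%.
- Pre/post: active-week mean minus weeks 1–2 mean.
- Baseline-adjusted: variance (2/60)[Var(post) − Cov(post, base)²/Var(base)].

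| Test and true effect | 13 weeks | 6 weeks |
|---|---|---|
| Slope, constant 650, exchangeable | 77–97% | 89–99% |
| Slope, constant 650, AR(1) data, independence or exchangeable working | 31–38% | 67–81% |
| Slope, constant 650, AR(1) data and working | 49–53% | 63–74% |
| Slope, fade 975 to 325, exchangeable | 5% | 46–74% |
| Slope, fade 975 to 325, AR(1) data | 5–13% | 23–38% |
| Pre/post, mean effect 650 | 88–100% | 87–100% |
| Baseline-adjusted mean, mean effect 650 | 99% or more | 98–100% |

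Slope rows include weeks 1–2. If the effect rises from 325 to 975, slope power at 13 weeks is 83–100%.

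**4. Efficiency of pre/post.** The variance of the adjusted contrast divided by that of the change score is 0.27–0.79 at 13 weeks and 0.52–0.83 at 6.

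**5. If 1200 is the SD of a participant's active-period average.** At 13 weeks with a constant effect, power is 13–86% for the slope, 35–100% for pre/post and 85–100% for the adjusted contrast. The 35% is an extreme: it needs a weekly SD of about 2,450 kcal, against a mean of 765 × 2.5 = 1,912.5 kcal/week from the power section's figures. The plan does say that its participants eat out more often than that.

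**The case against.** The best defence is that the plan is less open than it looks. It names trajectories as the target and includes a Time×Treatment term, so β3 is the likely test. Pre/post is a natural coding for it, because the plan labels weeks 1–2 as baseline. On that coding β3 is the powered quantity, and power is 87–100% with all weeks used and 1200 as a weekly SD. Preferring baseline adjustment to a change score is then a matter of efficiency, not the correction of an error. All of this stands. But pointing to β3 does not fix what it measures, and the same wording about trajectories also supports linear week.

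Two stronger readings are tempting and should be resisted. A reader might infer that the trial is underpowered. The documents do not support that: 60 per group exceeds what a two-group comparison of means needs, and power is adequate on many codings. A reader might also infer that the primary test cannot see a benefit that fades. The exact zero belongs to one fade over 13 weeks; over 6 weeks the same fade gives 86.7 per week and 23–74% power. That is a real loss but not a null effect.

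Baseline adjustment also has its own difficulties. Participants may know their group before weeks 1–2 end, so the covariate could be affected by assignment. Some participants may have no data from those weeks. The fix has to deal with both.

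**Conclusion.** The point holds as a gap in specification that should be fixed. Time, the unit of Y, the deciding coefficient and the role of weeks 1–2 are undefined. That choice determines whether the primary test addresses a 650 kcal/week mean difference.

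On pre/post coding there is no mismatch of target, only a loss of efficiency. On linear-week coding the stated 80% power does not describe the test. For the same mean benefit of 650, power at 13 weeks with weeks 1–2 included can be as high as 97% under a constant effect or as low as about 5% under the fade. It is 5% under a constant effect if the line starts at week 3.

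The omissions and the coefficients 39.3, 148.6 and 0 need no assumed correlation, given independence or exchangeable working correlation and complete weekly data. The power figures do rest on assumptions: the correlation ranges, the shape of the effect, 1200 as a weekly SD, complete data and the length of follow-up. The size of the loss is therefore uncertain.

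**What to change.** Before the data are examined:

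1. Define Y as kcal purchased per week. Define the active weeks as week 3 to the end of follow-up, once the three-month and six-week statements are reconciled.
2. Make the primary test the arm difference in mean kcal/week over the active weeks. Fit a GEE to those weeks with robust standard errors, week indicators, Treatment and the participant's weeks 1–2 mean as covariate, and test the Treatment coefficient. Name the working correlation as independence or exchangeable; with complete data Treatment is then the plain average difference over the active weeks.
3. Tie the power statement to this contrast and say what 1200 is the SD of.
4. Report the Time×Treatment slope as secondary, with Time defined.
5. State whether participants learn their group before weeks 1–2 end. Because C.3.b allows this, also report the contrast without the covariate. Its power is 92–100% at 6–13 weeks if 1200 is a weekly SD, and 84% if it is the SD of the average.
6. Use a missing indicator or a simple imputation for participants with no weeks 1–2 data, so that none are dropped.

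Defining Time as pre/post and naming β3 would also close the ambiguity, at the efficiency cost shown in step 4 of the working.

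The change is to analysis wording only, with no new data or participants. The price is less sensitivity than the slope in some settings where the effect grows. At 13 weeks, the slope's efficiency relative to the adjusted contrast is 0.68–1.24 (exchangeable) or 0.29–0.51 (AR(1)) for a rise from 325 to 975. For a rise from 0 to 1300 it is 1.54–2.79 or 0.66–0.95.

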## **C.3. Trial (Aim 3)**

**Rationale:** We will demonstrate the impact of using LIITAH on decreasing calories purchased from restaurants by adolescents, along with the number of visits to restaurants and the impact on their BMI.

**Overview:** The trial will consist of 2 arms (an intervention and a control arm) over the course of 3 months.

**Intervention Group** – Will receive the full version of the LIITAH app which consists of 5 components that allow 1) Enhanced Location Identification (ELI), 2) Self-report of Nutrients by Annotated Photos (SNAP), 3) delivery of individually and culturally tailored point of purchase (POP) prompts along with tailored messages sent at other times of day (determined by the participant), 4) use of the app in connection with parents, 5) goal setting capacity, and 6) a point system.

**Control Group** – Will receive a version of the app with only the ELI and SNAP components. Thus, it will detect their presence in a restaurant and allow users to document their purchases by submitting annotated photos, but it will not deliver any POP prompts encouraging them to make healthy choices, or messages at other times of day. It will not allow goal setting or assign points. The control parents will receive a version of the app with only the ELI system to detect when they are in an eating venue and the SNAP component so they can submit and annotated photo of any food they purchase from a restaurant for their adolescent.

**Primary Outcome** – Data regarding the number of calories purchased will be calculated based on the photos submitted and the calorie content as listed in the nutrition information from the restaurant. Comparisons will be made between groups to determine the impact of the program on calories purchased. In addition, 24-hour food recalls will be conducted in the baseline week and final week (3 per week) to provide a comparison assessment of caloric intake from restaurants and to explore changes in caloric intake overall.

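### The recall comparison in C.3.e measures restaurant calories eaten, not bought, so its agreement or disagreement with the photos cannot by itself show whether the photos are complete

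*Combined protocol and SAP*

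**What the plan says.** The primary outcome is defined in C.3.e: "Calories purchased (by and for adolescents) will be assessed using annotated photos, and nutrition data from restaurant menus". The item and size in the photo are valued from the menu, whether or not the adolescent finishes the food.

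The 24-hour recalls enter under Primary Outcome in C.3, with three in the baseline week and three in the final week, "to provide a comparison assessment of caloric intake from restaurants and to explore changes in caloric intake overall". C.3.d gives them a higher standing: "as a gold standard, pre-post 24-hour food recalls will be performed to assess caloric intake". Both places describe intake.

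The Secondary Analyses paragraph of C.3.e then changes the label. It begins "In additional exploratory analyses, using methods described above", and says that "changes in calories purchased from restaurants as assessed by the 24-hour recalls will also be examined to compare findings with the photo documentation method". No section has the recalls collect amounts bought, left over, shared or taken home, and none converts intake to purchases. No agreement measure or threshold is given.

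**The concern.** A photo total falls short of true purchases when a photo is not sent. A recall total falls short of true purchases when food is left or shared. These are different shortfalls, and a difference between the two summed totals shows only their net effect.

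At stake is how far the photo outcome can be trusted. Photo submission may not be equally complete in the two arms. Under Point system in C.1, adolescents earn points for sending a meal photo and extra points for a meal rated healthy. C.3 gives the control arm no points, and C.3.c activates the intervention features only in week 3, after the baseline period. The share eaten could also move, since C.3.c offers smaller portions as an example suggestion for venues without a menu. A check on the photos should detect a shift in capture by arm or period and should not be disturbed by a shift in the share eaten. The comparison as labelled does neither reliably. More recall days would not cure this, because the mismatch lies in what is measured and not in precision.

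**Working it through.** **Inputs from the documents.** C.3.e: "The average child consumes 765 calories per meal eaten away from the home and the average child eats 2.5 meals per week", so 765 × 2.5 = 1,912.5 kcal/week. Target difference: 650 kcal/week, SD 1,200, two-sided 0.05, 60 per group (C.3.e, Power). Eligibility: at least 3 restaurant meals per week (C.3.a).

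**Assumed, not in the documents.** c = share of purchased kcal that is photographed; f = share of purchased kcal that the adolescent eats. Both are varied from 0.7 to 1.0.

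**The plan's own figure.** The plan says that 60 per group "will have 80% power to detect a difference of 650 kcal/week". Recomputed, 80% power needs 54 per group by the normal approximation or 55 by the t-test, and 60 per group gives 83.7% by the t-test. The stated figure is therefore conservative. 60/(1 − 0.20) = 75 reproduces. Nothing below depends on this.

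**Single occasions.** Buy 765/0.8 = 956.25 kcal and eat 80% of it.
- Photo sent: photo − recall = 956.25 − 765 = +191.25.
- No photo: photo − recall = 0 − 765 = −765.

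The signs are opposite, so the two situations can be told apart occasion by occasion. After summing they can cancel: 765/191.25 = 4, so four photographed meals with leftovers offset one missed photo. That is capture 4/5 = 0.8, equal to the share eaten.

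**Changes, which are what the plan compares.** With true purchases P0 before and P1 after:
- photo change = c1·P1 − c0·P0
- recall change = f1·P1 − f0·P0

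Take P0 = 1,912.5, and let the other arm have no change in purchases or in either share. Each row is then also the between-group contrast (kcal/week).

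| Case | True change | c before → after | f before → after | Photo | Recall |
|---|---|---|---|---|---|
| 1 | −650 | 1 → 1 | 0.9 → 0.9 | −650 | −585 |
| 2 | −650 | 1 → 1 | 0.8 → 0.8 | −650 | −520 |
| 3 | −650 | 1 → 1 | 0.7 → 0.7 | −650 | −455 |
| 4 | −650 | 0.8 → 0.8 | 0.8 → 0.8 | −520 | −520 |
| 5 | 0 | 1 → 0.8 | 1 → 1 | −382.5 | 0 |
| 6 | 0 | 1 → 0.8 | 1 → 0.8 | −382.5 | −382.5 |
| 7 | 0 | 1 → 1 | 1 → 0.8 | 0 | −382.5 |
| 8 | −650 | 1 → 1 | 0.8 → 1 | −650 | −267.5 |

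- Cases 1 to 3: the photos are perfect, yet the recall reads 65 to 195 kcal/week (10% to 30%) low.
- Case 4: the methods agree exactly, yet a fifth of purchases is not photographed.
- Case 5: everything bought is eaten, and the recall does expose the missed photos.
- Case 6: the methods agree on a fall that did not happen.
- Cases 7 and 8: the photos are right and the recall disagrees. In case 8, 1,262.5 − 0.8 × 1,912.5 = −267.5.

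The 765 kcal figure is described as consumed, so using 1,912.5 as purchases is itself an assumption. Read as eaten with f = 0.8, purchases would be 1,912.5/0.8 = 2,391, and a shift of 0.2 in a share would be worth 478 instead of 382.5. Cases 1 to 4 do not depend on P0.

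**The case against.** The strongest reply is that this is a labelling slip in an exploratory comparison. C.3 already uses the right word, intake, and C.5 wants the recalls partly to see whether lower restaurant purchases are made up by eating at home, for which intake is the right quantity. With constant shares the comparison is only scaled and its direction does not change. When purchases fall and intake does not, both results are true, and the recall has not failed. All of this stands, and it limits the point.

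Four stronger readings are tempting and are not supported:
- **Level gaps as the error.** A reader might take the level gap between purchases and intake as the error in the comparison. With 765 kcal read as eaten and 2.5 meals per week, that gap is (765/f − 765) × 2.5, or 212 to 820 kcal/week for f = 0.9 to 0.7. The plan compares changes, so a constant share eaten costs only 10% to 30% of the effect.
- **A check that is passed or failed.** The plan sets no criterion.
- **Leftovers and missed photos cannot be told apart.** Single occasions differ in sign; only summed totals hide this.
- **The recalls are the only sight of missed photos.** The app also logs restaurant visits and how often pictures are sent (C.3.d). The plan does not set one against the other, and both come from the same app, but the data are collected.

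The reply does not remove the mismatch. The recall quantity is called a gold standard, is labelled as purchases, and is set beside the photo result without any means of separating the two shortfalls.

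**Conclusion.** The point holds as a mismatch of constructs in a stated comparison. Under a constant share eaten of 70% to 90%, a true 650 kcal/week effect reads 455 to 585 by recall with perfect photos. Under equal shares eaten and photographed, the methods agree while photos miss purchases. Shares that shift by arm or over time can create false agreement or false disagreement; a shift of 0.2 is worth about 380 kcal/week on the plan's weekly figure. Such shifts are plausible from the points and prompts, but the documents give no values for either share and do not settle the direction. If everything bought is eaten by the adolescent, the gap is zero and the comparison works as intended.

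A reader might infer that the primary analysis is compromised. It is not: the GEE on photo calories, its test and the sample size do not use the recalls. What is lost is the support the recalls could give to the photo measure. The change is worth making because it is cheap, not because the trial's main test depends on it.

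**What to change.** In the Secondary Analyses paragraph of C.3.e:

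1. Rename the recall quantity *restaurant calories eaten*, report it as a separate exploratory intake outcome, and state that it is not the reference for photo kcal. Limit the gold-standard description in C.3.d to intake.
2. Add a capture check. For each restaurant occasion reported on a recall day, record whether an adolescent or parent photo exists for that date. Supplement this with app-detected visits, since an occasion forgotten in the recall would otherwise drop out. Report the capture rate by arm and period.
3. On matched occasions only, compare items and sizes. State that photo kcal above recalled kcal is not counted as a photo error.

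**Cost.** No new visits, no change to sample size and no change to the primary model. The work is plan wording and linking recalls to photos. The linkage assumes that photo submission dates are stored, which the documents do not say.

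**Limits.** With meals spread evenly, three recall days hold 2.5 × 3/7 = 1.1 to 3 × 3/7 = 1.3 occasions per adolescent per period, or about 64 to 77 per arm with 60 completers. At 80% capture the standard error is √(0.8 × 0.2/64) = 0.05 per arm, ignoring clustering, and about 0.05 × √2 = 0.07 for a difference between arms. The check can show a large difference in capture at arm level and says nothing useful about individuals.
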